8.3. Clinical Laboratory Tests

8.3.1. Laboratory Value Definitions

Laboratory values and change from baseline values will be listed. Baseline will be determined according to Section 4.1.3. If there are multiple values that meet the criteria for baseline, additional rules may be provided after consultation with the medical monitor to delineate which value will be defined as baseline.

Laboratory test values outside of the normal range will be assessed for severity based upon the numerical component of CTCAE v5.0.

8.3.2. Laboratory Value Summaries

All test results and associated normal ranges from central laboratories will be reported in SI units. All tests with numeric values will have a unique unit per test. Any laboratory test results and associated normal ranges from local laboratories will be converted to SI units.

Severity grades will be assigned to laboratory test values based on the numerical component of CTCAE v5.0. CTCAE grades will be reported. Separate lists for abnormally high and abnormally low laboratory values will be provided when the laboratory parameter has both high and low grading criteria.

8.3.3. Potential Hy's Law Events

The participants with elevated alanine transaminase or aspartate transaminase $> 3 \times$ ULN range and alkaline phosphatase $< 2 \times$ ULN range accompanied by total bilirubin $> 2 \times$ ULN range at the same visit will be listed by cohort.

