**Table 5: Exclusionary Laboratory Values**

Laboratory Parameter		Exclusion Criterion
Hematology		
a	Platelets	$\leq 75 \times 10^9/L$ (transfusion allowed with a 2-week washout period)
b	Hemoglobin	$\leq 9.0 \text{ g/dL}$ (transfusion allowed with a 2-week washout period)
c	ANC	$\leq 1.5 \times 10^9/L$
Hepatic		
d	ALT	$\geq 3 \times \text{ULN}$ ( $> 5 \times \text{ULN}$ for liver metastasis)
e	AST	$\geq 3 \times \text{ULN}$ ( $> 5 \times \text{ULN}$ for liver metastasis)
f	Total bilirubin	$\geq 1.5 \times \text{ULN}$ ( $\geq 2.5 \times \text{ULN}$ if Gilbert's syndrome or liver metastasis)
g	Alkaline phosphatase	$\geq 3 \times \text{ULN}$
Renal		
h	Serum creatinine clearance	$\leq 30 \text{ mL/minute}$ based on Cockcroft-Gault formula
Chemistry		
i	Serum phosphate	$> \text{ULN}$
j	Serum calcium	Outside of normal range or serum albumin-corrected calcium outside of the normal range when serum albumin is outside of the normal range

10. History of calcium and phosphate hemostasis disorder or systemic mineral imbalance with ectopic calcification of soft tissues (exception: commonly observed calcifications in soft tissues such as the skin, kidney tendon, or vessels due to injury, disease, or aging in the absence of systemic mineral imbalance).
11. Gastrointestinal conditions/disorders that may raise gastric and/or small intestinal pH that could interfere with absorption, metabolism, or excretion of pemigatinib.
12. Inability to swallow and retain oral medication.
13. Clinically significant or uncontrolled cardiac disease, including unstable angina, acute myocardial infarction within 6 months before Day 1 of study drug administration, New York Heart Association Class III or IV congestive heart failure, and uncontrolled arrhythmia (participants with pacemaker or with atrial fibrillation and well-controlled heart rate are allowed).
14. History or presence of an abnormal ECG that, in the investigator's opinion, is clinically meaningful. A screening QTcF interval  $> 480$  milliseconds is excluded. For participants with an intraventricular conduction delay (QRS interval  $> 120$  ms), the JTc interval may be used in place of the QTcF with medical monitor approval. The JTc must be  $\leq 340$  milliseconds if JTc is used in place of the QTcF.

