

• Any safety assessments (eg, ECG, vital signs measurements), including those that worsen from baseline, considered clinically significant in the medical and scientific judgment of the investigator (ie, not related to progression of underlying disease) are to be reported as an AE.

• Abnormal laboratory test results are to be reported as an AE if they are considered clinically meaningful, induce clinical signs or symptoms, require concomitant therapy, or require changes in study drug. Whenever possible, a diagnosis (eg, anemia, thrombocytopenia) should be recorded in the eCRF rather than the abnormal laboratory test result (eg, low hemoglobin, platelet count decreased).

• Exacerbation of a chronic or intermittent pre-existing condition/disease, including either an increase in the frequency and/or intensity of the condition, is to be reported as an AE.

• New conditions detected or diagnosed after the start of study drug administration are to be reported as an AE.

• Signs, symptoms, or the clinical sequelae of a suspected drug-drug interaction are to be reported as an AE.

• Signs and/or symptoms from dosing errors of a study drug (eg, overdose) or a concomitant medication are to be reported as an AE.

• "Lack of efficacy," "disease progression," or "failure of expected pharmacological action" will not be reported as an AE or SAE. Such instances will be captured in the efficacy assessments.

• A condition that leads to a medical or surgical procedure (eg, endoscopy, appendectomy) will be reported as an AE if it occurs after obtaining informed consent. If the condition is present before entering the study, then it should be captured as medical history.

• Pre-existing diseases or conditions with expected fluctuations in signs or symptoms should be reported as an AE only if the investigator judges the fluctuation to have worsened more than expected during study participation.

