### DEFINITIONS

For the purpose of this process, definitions are as follows:

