#### Potential Hy's Law

An increase in AST or ALT  $> 3 \times$  ULN and total bilirubin  $> 2 \times$  ULN at any point during the study. The elevations do not have to be at the same time or within a specified timeframe.

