#### Hy's Law

An increase in AST or ALT  $\geq 3 \times$  ULN and total bilirubin  $> 2 \times$  ULN, where no other reason can be found to explain the combination of increases (eg, elevated serum ALP indicating cholestasis, viral hepatitis, another drug).

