## Potential Hy's Law Criteria Met

If the participant has had AST or ALT  $\geq 3 \times$  ULN AND total bilirubin  $> 2 \times$  ULN at any point in the study (the elevations do not have to be at the same time or within a specified timeframe), irrespective of ALP, please follow the instruction below:

- Have participant interrupt study drug.
- Notify Incyte study team without delay.
  - The investigator, or designee, should contact the medical monitor to discuss and agree upon an approach for the study participant's follow-up and the continuous review of data.
- Monitor the participant until liver biochemistry parameters and appropriate clinical symptoms and signs return to normal or baseline levels, or as medically indicated.
- Investigate the etiology of the event and perform any relevant diagnostic investigations as discussed with the medical monitor.
- Enter the laboratory data into the laboratory CRF as soon as possible.
- If at any time (in consultation with the medical monitor) the PHL case meets serious criteria, report it as an SAE using standard reporting procedures.

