## Actions After Review and Assessment

According to outcome of the review and assessment, please follow the instructions below:

If there **is** an agreed alternative explanation for the AST or ALT **and** total bilirubin elevations, a determination of whether the alternative explanation is an AE will be made and subsequently whether the AE meets the criteria for an SAE.

- If the alternative explanation is not an AE, record the alternative explanation on the appropriate CRF if possible.
- If the alternative explanation is an AE/SAE, record the AE/SAE in the eCRF accordingly and follow the standard study processes.
- Have participant resume study drug as per Protocol guidelines.

If it is agreed that there is no explanation that would explain the AST or ALT and total bilirubin elevations:

- Have participant permanently discontinue study drug and perform end-of-treatment procedures.
- Report an SAE (report term "Hy's Law").
  - The 'medically important' serious criterion should be used if no other serious criteria apply.
  - As there is no alternative explanation for the Hy's law case, a causality assessment of related should be assigned.
- If there is an unavoidable delay of over 3 weeks in obtaining the information necessary to assess whether or not the case meets the criteria for a Hy's law case, then it is assumed that there is no alternative explanation until such time as an informed decision can be made. Report an SAE (report term "Potential Hy's Law") applying serious criteria and causality assessment as per above.

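### SAP 8.3.3 and Listing 2.8.8 apply the protocol's name, potential Hy's law, to a narrower rule than Protocol Appendix D, without saying so

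*SAP*

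**What the plan says.** **SAP.** Section 8.3.3, headed Potential Hy's Law Events, sets three conditions: ALT or AST >3×ULN, ALP <2×ULN and total bilirubin >2×ULN. It ties them to one visit: "ULN range at the same visit will be listed by cohort". Listing 2.8.8 in SAP Appendix A has the same title. Section 8.3.3 does not cite Protocol Appendix D. Section 10.1, on changes to protocol-defined analyses, covers only the dropped futility and sensitivity analyses and the two dropped populations.

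**Protocol.** Appendix D introduces its terms with "For the purpose of this process, definitions are as follows". It defines potential Hy's law as AST or ALT >3×ULN and total bilirubin >2×ULN, and adds: "The elevations do not have to be at the same time or within a specified timeframe". The subsection on criteria being met repeats the timing rule and removes any ALP condition: "irrespective of ALP, please follow the instruction below". ALP enters only at the next stage. Under Hy's law, Appendix D gives as examples of other reasons for the combined rise "elevated serum ALP indicating cholestasis, viral hepatitis, another drug". Protocol 10.4.3 plans no Hy's law analysis.

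**The concern.** The two restrictions in the SAP, same visit and an ALP ceiling, are the two that Appendix D expressly sets aside. A reader of the study report who knows the protocol term will assume that Listing 2.8.8 shows the participants who met it. Under the SAP rule it need not.

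Two consequences follow. First, a participant whose drug was interrupted and whose case was jointly reviewed under Appendix D can be missing from the listing that bears that name. Second, Appendix D requires an SAE with the term Hy's Law when no explanation is found, and one with the term Potential Hy's Law in the situation that begins "If there is an unavoidable delay of over 3 weeks in obtaining the information necessary to assess". Such an event could appear in Listing 2.7.2 while Listing 2.8.8 is empty. This mismatch would arise mainly when the elevations fall at different visits or the review is delayed, because raised ALP is itself a named alternative explanation.

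**Working it through.** The plan gives no figure to reproduce, so the check is one of logic. All values are multiples of ULN.

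**The rules side by side**

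| Condition | SAP 8.3.3 | Appendix D, definition | Appendix D, criteria met |
|---|---|---|---|
| ALT or AST | >3 | >3 | ≥3 |
| Total bilirubin | >2 | >2 | >2 |
| Timing | same visit | any time in the study | any time in the study |
| ALP | <2 | no condition | no condition |

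Any record that meets the SAP column also meets both Appendix D columns. The reverse fails, as these hypothetical cases show:

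| Case | SAP | Definition (>3) | Criteria met (≥3) |
|---|---|---|---|
| ALT 4 at visit 1; bilirubin 2.5 at visit 2; ALP 1 at both | no | yes | yes |
| One visit: ALT 4, bilirubin 2.5, ALP 2.5 | no | yes | yes |
| One visit: ALT exactly 3, bilirubin 2.5, ALP 1 | no | no | yes |
| One visit: ALT 4, bilirubin 2.5, ALP 1 | yes | yes | yes |

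**Exhaustive check on a grid.** Take ALT/AST in {1, 3, 3.5}, bilirubin in {1, 2, 2.5} and ALP in {1, 1.99, 2, 3}. That gives 3 × 3 × 4 = 36 states per visit and 36² = 1296 two-visit profiles.

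- SAP rule: 2 qualifying states per visit, so 36² − 34² = 1296 − 1156 = 140 profiles.
- Appendix D with >3: 1296 − 24² − 24² + 16² = 1296 − 576 − 576 + 256 = 400. Here 24 states lack the transaminase elevation, 24 lack the bilirubin elevation and 16 lack both.
- Appendix D with ≥3: 1296 − 12² − 24² + 8² = 1296 − 144 − 576 + 64 = 640.
- Profiles that meet the SAP rule but not Appendix D: 0 under either wording.
- Profiles that meet the >3 wording but not the SAP rule: 400 − 140 = 260. Both elevations coincide at some visit, at any ALP, in 36² − 32² = 272 profiles. So 272 − 140 = 132 are lost through the ALP ceiling and 400 − 272 = 128 through timing.

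The grid counts show the logic only. They say nothing about how often such cases occur.

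**Size.** SAP 10.1 states that fewer than 10 participants were enrolled, so at most 9 can be affected and at least 0. The documents give no incidence.

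**Entry limits (Protocol Table 5)**

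- ALP excludes at ≥3, so a participant can enter with ALP from 2 to <3. While ALP stays there, SAP 8.3.3 cannot list that participant, whatever the other values.
- With liver metastasis, ALT and AST exclude only above 5. The bilirubin limit of 2.5 applies for Gilbert's "syndrome or liver metastasis". A participant with liver metastasis can therefore enter with ALT or AST >3 to 5 and bilirubin >2 to <2.5, which meets the Appendix D thresholds before the first dose. A listing based on Appendix D must therefore show baseline values.

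**The case against.** The best counter-argument is that nothing obliges the two rules to match. Appendix D defines its terms for its own case-management process, and Protocol 10.4.3 plans no Hy's law analysis. SAP 8.3.3 states its criterion in full, so nothing protocol-defined has been altered and section 10.1 had nothing to record. Detection does not rest on the listing either, because the investigator identifies cases by reviewing results from all previous visits. With so few participants, a reader can check each one by hand from the chemistry listings.

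Most of this stands. No protocol-defined analysis is changed, and a narrower screen is a legitimate choice. Values are listed and CTCAE-graded (SAP 8.3.1 and 8.3.2; Listings 2.8.2 and 2.8.6), and dose interruptions are listed (SAP 6.3). On-drug cases should usually reach Listings 2.7.1 and 2.7.6: Appendix D requires interruption, and Protocol 9.1 makes a laboratory abnormality that requires a change in study drug an adverse event.

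It does not justify giving the protocol's term to a different rule without saying so. Combining elevations across visits is the work such a listing should do, and the reader would have to do it by hand.

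Two further objections concern the remedy. The Appendix D rule also picks up baseline-only and widely separated elevations; this is true and is met by extra columns. The filter also cannot be final while Appendix D gives two transaminase thresholds. That is true as well, but it matters only for a value of exactly 3×ULN.

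**Conclusion.** The concern holds and is minor. One name covers two rules, the SAP rule is a strict subset of the protocol rule, and the SAP does not disclose this. Listing 2.8.8 can omit protocol-defined cases when the elevations fall at different visits or when ALP is ≥2×ULN. An empty listing is not evidence that no protocol-defined case occurred.

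Between 0 and 9 participants could be affected, and the true number may be zero. No estimate, interval or test changes. The conclusion rests only on the wording of the two documents and on the SAP's statement of enrolment; it assumes no event rate.

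**What to change.** Replace the selection rule in SAP 8.3.3 with wording such as: *Participants who meet the Protocol Appendix D transaminase threshold and have total bilirubin >2×ULN at any point on study, at the same visit or not and irrespective of ALP, will be listed by cohort.*

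Show in Listing 2.8.8:

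- baseline values;
- the date of each elevation;
- ALP as a multiple of ULN;
- a same-visit flag;
- a flag for before or after the first dose.

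The narrower subset and the baseline-only elevations can then be read directly.

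If the sponsor keeps the present rule, retitle the listing and state how it differs from Appendix D. This is the weaker option: it removes the naming conflict but leaves no display of the protocol-defined cases.

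Separately, the sponsor must reconcile the transaminase wording within Appendix D. It is >3×ULN in the definition of potential Hy's law and in the identification step, but ≥3×ULN in the definition of Hy's law and in the subsections on criteria met and not met. The listing should follow the reconciled text.

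The cost is one SAP sentence, one programming filter and a few listing columns, all from data already collected, plus the reconciliation of Appendix D before the filter is final.

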8.4. Vital Signs

Values at each scheduled visit for vital signs, including weight, systolic blood pressure, diastolic blood pressure, pulse, temperature, and respiratory rate, will be listed.

Criteria for clinically notable vital sign abnormalities are defined in [Table 4](#). The abnormal values for participants exhibiting clinically notable vital sign abnormalities will be listed along with their cohort. Alert vital signs are defined as an absolute value outside the defined normal range and percentage change from baseline greater than 25%. Note that the definition of alert vital signs does not apply for body temperature and weight. The abnormal values for participants exhibiting alert vital sign abnormalities will be listed.

Table 4: Criteria for Clinically Notable Vital Sign Abnormalities

Parameter	High Threshold	Low Threshold
Systolic blood pressure	> 155 mmHg	< 85 mmHg
Diastolic blood pressure	> 100 mmHg	< 40 mmHg
Pulse	> 100 bpm	< 45 bpm
Temperature	> 38°C	< 35.5°C
Respiratory rate	> 24 breaths/min	< 8 breaths/min

8.5. Electrocardiograms

Twelve-lead ECGs including heart rate (HR), PR, QRS, QT and QTc intervals will be obtained for each participant during the study. Values at each scheduled visit, change, and percent change from baseline will be listed for each ECG parameter. Baseline will be determined as the average of all nonmissing values before the first administration of pemigatinib.

Criteria for clinically notable ECG abnormalities are defined in [Table 5](#). The ECG values will also be considered abnormal if the absolute percentage change from baseline is more than 25% (QRS 30%). Participants exhibiting ECG abnormalities will be listed with study visit and assigned cohort. Abnormal values for participants with alert ECG values, defined as both the absolute value and the percentage change from baseline being outside the defined normal ranges, will be identified and listed.

Table 5: Criteria for Clinically Notable Electrocardiogram Abnormalities

Parameter	High Threshold	Low Threshold
PR	> 220 ms	< 75 ms
HR	> 100 bpm	< 45 bpm
QT	> 500 ms	< 300 ms
QRS	> 120 ms	< 50 ms
QTc	> 460 ms	< 295 ms

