**Table 7: Guidelines for Interruption and Restarting of Study Drug (Continued)**

Adverse Event	Action Taken
• Recurrent Grade 2 toxicity	Step 1: Interrupt pemigatinib up to 2 weeks (14 days), until toxicity resolves to $\leq$ Grade 1 Step 2: If related to pemigatinib, restart pemigatinib at the next lower dose level. Monitor as clinically indicated and if AE persists, consider further dose reduction.
• Any Grade 3 toxicity	Step 1: Interrupt pemigatinib up to 2 weeks (14 days), until toxicity resolves to $\leq$ Grade 1. Step 2: Restart pemigatinib at same dose. If assessed as related to pemigatinib, restart pemigatinib at the next lower dose; monitor as clinically indicated. If AE persists for more than 1 cycle, consider a dose reduction.
• Any recurrent Grade 3 toxicity after 2 dose reductions.	Discontinue pemigatinib administration and follow-up per Protocol. (Exceptions require approval of sponsor.)
• Any other Grade 4 toxicity. • QT/QTc to $>$ 500 ms or to $>$ 60 ms over baseline.	Discontinue pemigatinib administration and follow-up per Protocol.

For participants who present with possible or confirmed SRD/RPED based on OCT, the guidelines in [Table 7](#) should be followed. It is recommended to discuss the findings with the sponsor's medical monitor before making changes to the participant's treatment.

Per CTCAE v 5.0, retinal detachment is graded as 3 (macular sparing) and 4 (macula-off), but this refers to rhegmatogenous retinal detachment (when a hole occurs in the retina). There is no grading for SRD/RPED (no hole in the macula, just fluid accumulation). Therefore, grading should be based on the CTCAE v5.0 term of retinopathy.

The starting dose of pemigatinib will be 13.5 mg QD, intermittent dosing regimen (2 weeks on treatment and 1 week off treatment). Dose reductions should follow as noted below:

- Starting dose: 13.5 mg QD intermittent dosing
- First dose reduction: 9 mg QD intermittent dosing
- Second dose reduction: 4.5 mg QD intermittent dosing

Dose reductions below 4.5mg QD are not allowed. Following a dose reduction and resolution of pemigatinib-related toxicities, a participant's dose may be returned to the starting dose at the discretion of the investigator and in consultation with the sponsor's medical monitor.

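### The SAP's QTc abnormal and alert flags do not match the protocol's QTc discontinuation criterion, so the flagged ECG listings can omit a participant who met it

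*SAP*

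**What the plan says.** Protocol Table 7 (section 6.5.1) names the event "QT/QTc to $>$ 500 ms or to $>$ 60 ms over baseline" and gives the action "Discontinue pemigatinib administration and follow-up per Protocol".

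SAP 8.5 sets reporting rules for ECGs:

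- Table 5 gives the absolute QTc limits: "QTc > 460 ms < 295 ms". A 500 ms limit appears in that table only for uncorrected QT.
- A relative rule is added: "The ECG values will also be considered abnormal if the absolute percentage change from baseline is more than 25% (QRS 30" (the QRS figure is likewise a percentage).
- An alert is "defined as both the absolute value and the percentage change from baseline being outside the defined normal ranges".
- For the reference value, "Baseline will be determined as the average of all nonmissing values before the first administration of pemigatinib".
- "Values at each scheduled visit, change, and percent change from baseline will be listed for each ECG parameter".

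SAP Appendix A plans three ECG listings: all values (2.10.1), abnormal values (2.10.2) and alert values (2.10.3). It plans no ECG table. Protocol 10.4.3 promises a listing of participants with clinically notable ECG abnormalities, and SAP 8.5 is where that term is defined.

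**The concern.** The protocol's criterion is expressed as an absolute level of 500 ms and an absolute rise of 60 ms. The SAP has no flag in milliseconds of change and no 500 ms flag for QTc. It uses a lower absolute level together with a percentage change, and a 25% change in QTc is a much larger move than 60 ms at ordinary baselines. The highest reporting tier, the alert, requires both conditions at once.

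ECGs belong to the secondary safety endpoint (Protocol Table 4). A reader of the study report would expect the abnormal and alert listings to pick out at least those participants whose QTc met the protocol's discontinuation criterion. If they do not, such a participant has to be found by working through the full listing by hand. The case that matters most is a participant who met the criterion but was not discontinued, because listings of discontinuations would not show that person.

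**Working it through.** The documents give no figure on this point to reproduce. The check compares the rules directly.

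**Inputs.** B is baseline QTc and V is on-treatment QTc, both in ms.

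- Protocol criterion (Table 7): V > 500, or V − B > 60.
- SAP abnormal flag (8.5, Table 5): V > 460, or V < 295, or |V − B|/B > 0.25.
- SAP alert: (V > 460 or V < 295) and |V − B|/B > 0.25.

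Two readings are assumed. B is the SAP's average of pre-dose values, and the percentage range in the alert definition is the 25% rule.

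**Step 1: where 25% equals 60 ms.** 60 / 0.25 = 240 ms. At any higher baseline the percentage rule needs a larger rise than the protocol does: more than 90 ms at B = 360, 100 ms at 400, 110 ms at 440 and 120 ms at 480.

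**Step 2: abnormal flag.** A rise above 60 ms is missed when B + 60 < V ≤ the smaller of 460 and 1.25 × B.

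- This range is empty when B ≤ 240, because the 25% rule is then at least as strict.
- It is also empty when B ≥ 400, because B + 60 is then at least 460 and every such rise crosses the 460 ms limit.
- Misses therefore occur only for 240 < B < 400.
- Any V > 500 exceeds 460, so that part of the criterion is always caught.

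**Step 3: alert flag.** For a rise, an alert needs V > 460 and V > 1.25 × B. Rises above 60 ms are missed when B + 60 < V ≤ the larger of 460 and 1.25 × B. Values above 500 ms are missed when 500 < V ≤ 1.25 × B, which requires B > 500 / 1.25 = 400.

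**Step 4: missed values, in whole ms.**

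| B | 1.25 × B | Rise > 60 ms missed by abnormal flag | Rise > 60 ms missed by alert | Values > 500 ms missed by alert |
|---|---|---|---|---|
| 300 | 375 | 361–375 | 361–460 | none |
| 360 | 450 | 421–450 | 421–460 | none |
| 380 | 475 | 441–460 | 441–475 | none |
| 399 | 498.75 | 460 only | 460–498 | none |
| 400 | 500 | none | 461–500 | none |
| 420 | 525 | none | 481–525 | 501–525 |
| 440 | 550 | none | 501–550 | 501–550 |
| 480 | 600 | none | 541–600 | 501–600 |

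**Step 5: examples.**

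- 390 to 455 ms: +65 ms, 65/390 = 16.7%, value below 460. The protocol criterion is met, and there is no flag of either kind.
- 430 to 510 ms: +80 ms, 80/430 = 18.6%. Both parts of the protocol criterion are met. The value is abnormal but not an alert, because an alert would need V > 1.25 × 430 = 537.5 ms.
- 360 to 455 ms: +95 ms, 95/360 = 26.4%. The percentage rule alone makes this abnormal, so that rule is looser than the protocol's but does detect some qualifying rises.

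**The case against.** The strongest reply is that nothing is hidden. Listing 2.10.1 prints value, change and percent change for each ECG parameter at scheduled visits, so the 390 to 455 ms case appears there as +65. A participant taken off drug is also visible through the listed reason for treatment discontinuation (Listing 2.1.1) and the listing of adverse events leading to interruption, reduction or discontinuation (2.7.6). ECG abnormalities that the investigator judges clinically significant are reported as adverse events (Protocol 8.3.4). Fewer than 10 participants were enrolled (SAP 10.1), so the full listing can be read line by line. Finally, Table 7 governs treatment and SAP Table 5 governs display, and Protocol 10.4.3 does not require the two sets of thresholds to be the same.

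Most of this stands, and it limits the point to flagging. Two parts do not fully answer it. The discontinuation listings show only participants who were stopped, not one who met the criterion and continued. The SAP sentence behind Listing 2.10.1 refers to scheduled visits, whereas Protocol 8.3.4 allows additional ECGs when clinically indicated, and SAP 8.5 does not say how those are shown.

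A reader might draw four stronger conclusions that the documents do not support:

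- *That 2.10.2 and 2.10.3 are the only planned QTc output.* Listing 2.10.1 exists.
- *That the safety endpoint understates QTc prolongation.* No QTc rate or count is planned, so no estimate is biased.
- *That the percentage rule cannot detect the protocol's criterion.* It catches any rise above 25%, such as 360 to 455 ms.
- *That a 460 ms limit is a defect because of the entry rule "A screening QTcF interval $> 480$ milliseconds is excluded".* A display limit below an eligibility limit only makes the flag more sensitive, and the two limits serve different purposes.

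**Conclusion.** The mismatch is real but narrow. The abnormal listing can omit a participant with a QTc rise above 60 ms only if baseline is above 240 and below 400 ms, the value is at most 460 ms and the change is at most 25%. It omits none at baselines of 400 ms or more and no value above 500 ms. The alert listing omits rises between 60 ms and 25% of baseline at any realistic baseline. At baselines above 400 ms it also omits some values above 500 ms, although those participants remain in the abnormal listing.

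No data are lost and no analysis result changes. With fewer than 10 participants the practical effect is small, and the documents do not show whether anyone was affected. The conclusion rests on the SAP's baseline definition and on reading the alert rule as requiring both conditions. The SAP flags do not govern treatment, and no view is taken here on which threshold is clinically right. The point is that the two documents use different QTc criteria and should be reconciled for reporting.

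**What to change.** Reconcile SAP 8.5 with Protocol Table 7 by adding two display flags that repeat the protocol's existing criterion: QTc above 500 ms, and QTc increase of more than 60 ms over baseline. Let either flag place the value in both the abnormal and the alert ECG listings (2.10.2 and 2.10.3). Label the correction as QTcF, which is the interval that Protocol 8.3.4 has the ECG machine measure; SAP Table 5 says only QTc. The existing 460 ms, 295 ms and percentage rules may stay.

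With these flags, every case in the table above is marked by construction, including 390 to 455 ms and 430 to 510 ms. The cost is a short addition to SAP 8.5 and Table 5 and two derived variables from ECG data already collected. No new assessment, no new listing and no change to any treatment rule is needed.
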